## 6.2.2. Fatigue Severity Scale

The FSS is a 9 item Patient Reported Outcome assessment that covers physical, social, and cognitive effects of fatigue such as function, work, and motivation (Krupp et al 1989). The 9 items are summed and then averaged to produce a global score. Each item has seven choices from strongly disagree to strongly agree (1-7), and the recall period is the past week. The FSS takes approximately 2-3 minutes to complete. It has demonstrated content, construct, and

criterion validity and has demonstrated the ability to detect change (Hewlett et al 2011). The FSS has been used to evaluate fatigue in patients with DM (Hermans et al 2013; Laberge et al 2009). The FSS is provided in Appendix G.

### 6.2.3. Cogstate Computerized Cognitive Battery Tests

Cognition will be assessed using the Cogstate Computerized Cognitive Battery Tests, a standardized, fully automated, modular battery of tests designed specifically for repeated assessment with minimal practice effects (Collie et al 2003; Falleti et al 2006). The test battery has a short administration time, contains multiple alternate forms, and yields data appropriate for detecting cognitive change. In this study, the cognitive domains of psychomotor function, attention, and working memory will be assessed using the Detection, Identification, and One Back tests, respectively. Patients will undergo two short training sessions to become familiar with the test.

### 6.2.3.1. Cogstate Detection Test (Psychomotor Function)

The Cogstate Detection Test is a computerized measure of psychomotor function and uses a validated simple reaction time (RT) paradigm with playing card-like stimuli displayed on a computer screen. In this test, the playing cards all depict the same image. The patient is asked to press the "yes" key as soon as the card in the center of the screen turns face up. The software measures the speed and accuracy of each response. The main outcome measure for the test is speed of performance (mean of the log10-transformed reaction times for correct responses). Decreasing scores represent improved test performance.

### 6.2.3.2. Cogstate Identification Test (Attention)

The Cogstate Identification Test is a computerized measure of visual attention and uses a validated choice RT paradigm with playing card-like stimuli displayed on a computer screen. In this test, the playing cards are all either red or black. The patient is asked whether the card displayed in the center of the screen is red. The patient responds by pressing the "yes" key when the card is red and "no" when it is black. The software measures the speed and accuracy of each response. The main outcome measure for the test is speed of performance (mean of the log10-transformed reaction times for correct responses). Decreasing scores represent improved test performance.

### 6.2.3.3. Cogstate One Back Test (Working Memory)

The Cogstate One Back Test is a computerized measure of working memory and uses a validated n-back paradigm with playing card stimuli displayed on a screen. The patient is asked whether the card displayed in the center of the screen is the same as the card presented immediately previously. The patient responds by pressing the "yes" or "no" key. The software measures the speed and accuracy of each response.

### 6.2.4. Myotonic Dystrophy Health Index

The MDHI is a disease-specific, patient-reported outcome measure for DM1. This instrument has been validated in a manner consistent with the FDA guidance on patient reported outcomes and is designed to accurately reflect the overall burden of disease from the patient's perspective. It

focuses on the major symptoms experienced by patients with DM1 and prioritizes them by their relative importance to patients. It is scored on a scale of 0-100, with a higher score representing a higher burden of disease; subscales within the instrument are weighted so that certain themes, including sleep, fatigue, and cognitive impairment, have greater impact on the overall score. (Heatwole et al 2014 and Heatwole et al 2016). Overall, the MDHI is optimally suited to detect small but clinically relevant changes in several key areas of DM health over the course of a treatment trial and has been recognized by the DM working group of National Institute of Neurological Disorders and Stroke (NINDS) as one of the key assessments that should be used in clinical trials of patients with DM1 (NINDS 2014). The MDHI addresses several areas of health relevant to the condition. The tool consists of multiple symptom-related questions grouped into several themes including fatigue, sleep, and cognitive impairment. Subscales of the MDHI measure patients' perception of their health as it relates to mobility, upper extremity function, ability to do activities, fatigue, pain, gastrointestinal issues, vision, communication, sleep, emotional issues, cognitive impairment, social satisfaction, social performance, myotonia, breathing, swallowing, and hearing. The MDHI is provided in Appendix H.

### 6.2.5. Epworth Sleepiness Scale

The ESS is a questionnaire with eight questions in which respondents are asked to rate, on a 4point scale (0-3), their usual chances of dozing or falling asleep while engaged in eight different activities. The questionnaire is a validated measure with high specificity and sensitivity for assessing subjective sleepiness in narcolepsy (Johns 1991). It has been deemed appropriate for the assessment of EDS in patients with DM1 by the NINDS and is recommended for use in this population (NINDS 2014). The total ESS score (sum of 8 item scores) can range from 0 to 24; the total score gives an estimate of the person's 'average sleep propensity' (ASP), across a wide range of activities in their daily lives. The higher the ESS score, the higher that person's ASP in daily life or their 'daytime sleepiness'. The ESS is provided in Appendix I.

## 6.2.6. Clinical Global Impression of Severity of Excessive Daytime Sleepiness

The CGI-S is a one-item, 4-point Likert-type rating scale and is a widely used assessment in clinical psychopharmacology trials to assess severity of illness. At Baseline, Week 11/EOT in the Double-Blind Treatment Phase, and at each on-site study visit in the OLE Phase, the Investigator will rate his/her impression of the severity of the patient's current overall clinical status related to EDS relative to the Investigator's experience with this patient population, based on observed and reported symptoms and function. The CGI-S asks the clinician one question: "Considering your total clinical experience with this particular population, please rate the patient's overall severity of EDS at this time". The responses for this investigator-completed scale range from "none" to "severe". The CGI-S is provided in Appendix J.

## 6.2.7. Patient Global Impression of Severity of Excessive Daytime Sleepiness

The PGI-S is a one-item, 4-point Likert rating scale completed by the patient to rate their overall impression of their EDS. At Baseline, Week 11/EOT in the Double-Blind Treatment Phase, and at each on-site study visit during the OLE Phase, patients will be asked to rate their impression of the overall severity of their symptoms of EDS over the past week, based on the impact EDS has on the patient's ability to function during the day. The PGI-S of EDS asks the patient to rate their likelihood of falling asleep during daytime activities over the past week. The responses for the

patient-completed scale range from "none" to "high" The PGI-S for EDS is provided in Appendix K.

### 6.2.8. Sustained Attention to Response Task

The SART is a measure of sustained attention, which is the ability to focus on an activity or stimulus over a long period of time, or to direct focus and cognitive ability on specific stimuli. It is a computer-based go/no-go task that requires participants to withhold behavioral response to a single, infrequent target presented amongst a background of frequent non-targets. Both accuracy and response speed, quantified as RT, are important. The SART was developed to investigate lapses of sustained attention in individuals with neurological impairment. It also proved to be a useful tool to investigate sustained attention in a number of other clinical conditions including sleep disorders (van Schie et al 2012). Validation of the SART was done in patients with narcolepsy and is based on a comparison between patients with narcolepsy and healthy controls (Fronczek et al 2006). The SART is also considered a useful tool to measure treatment efficacy in narcolepsy (van der Heide et al 2015).

### 6.2.9. Maintenance of Wakefulness Test

The MWT, a daytime polysomnographic procedure for the evaluation of daytime somnolence/wakefulness, is used to assess an individual's ability to stay awake while resisting the pressure to fall asleep. It is used clinically in disorders with excessive somnolence such as narcolepsy and sleep apnea syndrome (Browman et al 1983; Browman et al 1986; Poceta et al 1992; Sangal et al 1992a). The MWT evaluates the magnitude of sleepiness in relationship to the underlying wakefulness system's functioning. It has also been utilized to examine treatment efficacy (Sangal et al 1992b). When conducting the MWT, patients are administered four 40-minute sessions at 2-hour intervals according to the validated standard (Doghramji et al 1997), with the initial session beginning two hours after wakening.

# 6.3. Safety Assessments

### 6.3.1. Adverse Events

All AEs, regardless of causality or seriousness, will be collected from the time the patient provides written informed consent through 30 days after the final dose of study drug (Safety Follow-up TC, Section 7.4). Adverse event recording at the Safety Follow-up TCs will include inquiries regarding signs and symptoms of arrhythmia, any other cardiac manifestations [e.g., syncope], and psychiatric events [e.g., suicidality, compulsive behavior, anxiety]). Additional safety information, including the definition of an AE/SAE and reporting requirements is provided in Section 8.

Clinically significant findings for laboratory test results, vital signs, Holter monitoring, ECGs, and abnormal physical examination findings should be recorded as AEs; a clinical diagnosis, rather than the changes in laboratory analyte or other assessment should be recorded.

### 6.3.2. Physical Examinations

Full or abbreviated physical examinations will be performed at study visits as detailed in Section 7. Full physical examinations will include an evaluation of the head and neck as well as

CV, respiratory, gastrointestinal, neurological, dermatological, and musculoskeletal systems. Abbreviated physical examinations will be performed based on patient-reported symptoms.

Height and weight will be measured using standardized methods. Height will be recorded at Screening. Body weight will be recorded at Screening (Visit 1), Baseline (Visit 2), EOT (Visit 5), and all on-site study visits during the OLE Phase, as detailed in Section 7.

### 6.3.3. Vital Signs

Vital signs will include blood pressure, HR, respiratory rate, and body temperature and will be measured at on-site study visits as detailed in Section 7. Patients should be resting for at least 5 minutes before measuring vital signs.

Vital sign measurements will be performed before blood samples are collected for clinical laboratory testing.

### 6.3.4. Holter Monitoring and 12-Lead Electrocardiograms

Holter monitoring and triplicate 12-lead ECGs will be performed at Screening and during the Double-Blind Treatment Phase and OLE Phase of the study as detailed in Section 7. The Holter monitoring performed at Screening and the ECGs performed at Screening and Baseline will determine whether an exclusionary CV issue is present, and assessment at later time points during the study is designed to detect any changes in CV parameters and to detect the development of arrhythmias.

A core ECG laboratory will manage all ECG and Holter monitoring activities, including standardization and training of the technical staff at all study sites in proper electrode placement, operation of the hardware, and management of patients during testing. Electrocardiogram and Holter monitoring data will be transmitted electronically to the core laboratory and will be promptly interpreted by trained cardiologists. Pre-specified criteria for QT, QRS duration, AVB, and arrhythmias will trigger immediate notifications.

## 6.3.4.1. Holter Monitoring

Holter monitoring will be performed during Screening (Visit 1) and Visit 3 (Day 22) during the Double-Blind Treatment Phase. Patients will be fitted with a Holter monitor, which they will wear for 24 hours before returning the device to the study site via courier or directly to the site if able, as detailed in a separate instructional document.

In the OLE Phase, to monitor for arrhythmias at the time patients have reached their 35.6 mg dose of pitolisant, Holter monitoring (24-hour) will be initiated at the end of the OLE Titration Period at Visit 6 (Day 99).

For all abnormal Holter monitor findings considered clinically significant by the Investigator, additional evaluation, including an unscheduled ECG, is required (the ECG can be performed locally); abnormal findings on follow-up ECGs should be addressed as detailed in Section 6.3.4.2.

The Holter monitor must be placed on the patient and continuous recording started as the ECG data will be taken from the Holter monitor recording.

### 6.3.4.2. 12-Lead Electrocardiograms

Triplicate 12-lead ECGs will be obtained for all patients at every on-site study visit as detailed in Section 7. Patients should be resting for at least 5 minutes before each 12-lead ECG is performed. At Visit 3 and Visit 5, triplicate 12-lead ECGs will be performed with every blood sample collected for PK analyses, as detailed in Section 7.2.4.1 and Section 7.2.4.4, respectively. The ECGs should be done prior to and within 15 minutes of the blood draw for PK analyses.

For clinically significant ECG findings, a follow-up ECG should be performed within 24 hours and again 7 days later to ensure the abnormality is not worsening. Follow-up 12-lead ECGs may be performed locally and sent to the Investigator for assessment; the Investigator will submit all ECGs done locally to the central ECG vendor.

The following ECG abnormalities should be promptly addressed by the Investigator and will require discontinuation of study drug (Section 4.4.1):

• Any ECG finding that demonstrates QT prolongation (i.e., QTcF >500 msec or an increase >60 msec) regardless of resultant QTc value

In addition to a potential QT prolongation, the Medical Monitor should be consulted for:

- PR interval >300 msec, QRS duration >140 msec, or any increase from baseline in PR or QRS greater than 50% or 40%, respectively
- HR increase >65% over baseline or decrease >40% compared with baseline

In the event of these clinically significant abnormal PR interval, QRS duration, or HR ECG results, the ECG should be repeated as soon as possible and if done the next day, attempts should be made to perform the repeat ECG at the same time of day that the abnormal ECG was obtained. If the event persists or worsens, study drug may be interrupted for 2 to 3 days and the ECG will be repeated on the third day. If the abnormality has improved, study drug dosing may resume. If the condition persists or worsens after the study drug interruption, the Investigator, in consultation with the Medical Monitor, will decide whether treatment should be permanently discontinued.

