A core ECG laboratory will manage all ECG and Holter monitoring activities. All ECGs will be recorded in triplicate. All ECG and Holter data will be transmitted electronically to the core laboratory and will be promptly interpreted by trained cardiologists. Pre-specified ECG criteria for QT, QRS duration, AVB, and arrhythmias will trigger immediate notifications related to ECG and Holter monitoring abnormalities. Any ECG finding that demonstrates QT prolongation (i.e., QTcF >500 msec or an increase of >60 msec regardless of resultant OTc value) should be promptly addressed by the Investigator and will require discontinuation of study drug. In addition to a potential QT prolongation, the Medical Monitor should be consulted for PR >300 msec, QRS >140 msec, or any increase from baseline in PR or QRS greater than 50% or 40%, respectively. The Medical Monitor should also be consulted for any HR increase >65% over baseline or decrease >40% compared with baseline. The ECG should be repeated as soon as possible in the event of these clinically significant results; if done the next day, attempts should be made to perform the repeat ECG at the same time of day that the abnormal ECG was obtained. If the event persists or worsens, study drug will be interrupted for 2-3 days and the ECG will be repeated on the third day. If the abnormality has resolved (i.e., return to baseline values), study drug dosing may resume at the same dose as administered before the interruption (or, in the OLE Phase, resumed with dose adjustment per the Investigator's discretion). If the condition persists or worsens after study drug interruption (or after adjustment in the OLE Phase), treatment with study drug will be permanently discontinued and the subject will be referred to a cardiologist. In addition, in the event of an increase of >60 msec in OTc, study drug will be permanently discontinued, and the subject will be referred to a cardiologist. For all abnormal ECG or Holter monitoring findings considered clinically significant by the Investigator, a follow-up ECG should be performed within 24 hours and again 7 days later to ensure the abnormality is not worsening. These follow-up 12-lead ECGs may be performed locally.

Measurement of laboratory parameters (hematology, serum chemistry, and urine values) and vital signs will be performed at every on-site visit in the Double-Blind Treatment Phase and OLE Phase of the

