- 11. Has a diagnosis of moderate or severe renal impairment (eGFR ≥15 to ≤59 mL/minute/1.73 m^2) or moderate hepatic impairment (Child-Pugh B) at Screening or during the Double-Blind Treatment Phase.
- 12. Has a family history of sudden cardiac death, unexplained death, or death from a primary dysrhythmia potentially associated with QT prolongation in any family member (i.e., first degree relative such as parent, sibling, or offspring).
- 13. Has a history of unexplained syncope.
- 14. Has a history of long corrected QT interval (QTc) syndrome or corrected QT interval using Fridericia's formula (QTcF) >450 msec for males or >470 msec for females (QTcF = QT /  $3\sqrt{RR}$ ) sustained atrial fibrillation (AF) or left ventricular ejection fraction <50%.

- 15. Has a history of documented symptomatic arrhythmias (e.g., ECG, Holter monitor).
- 16. Electrocardiogram abnormalities during a 10-second, 12-lead ECG at Screening of first degree AVB (PR interval >220 msec), QRS >120 msec, heart rate (HR) <50 beats per minute (bpm), marked T-wave abnormalities, more than single atrial premature complexes (APCs) or premature ventricular contractions (PVCs), left bundle branch block, or Brugada pattern type 1.

Note: Patients with  $1^{st}$  degree AVB with a PR interval  $\geq$  220 msec, who are treated prophylactically with an allowable implanted device are not excluded from the study.

- 17. Based on Holter monitor, any episode of 3rd degree AVB, any prolonged episode of second degree AVB (>2 episodes during waking hours, >6 episodes during sleep), any prolonged episode of 2nd degree AVB (>10 seconds), any asystole longer than 3.5 seconds, any run of ventricular tachycardia (VT) >6 beats, frequent runs of non-sustained VT (>5/24 hour), >400 PVCs/24 hours, AF or paroxysmal AF, or frequent or complex atrial arrhythmias.
- 18. Has history of New York Heart Association (NYHA) class III or class IV heart failure.
- 19. Has an implanted defibrillator or implanted biventricular pacemaker.

Note: Patients with implanted univentricular pacemakers that are used prophylactically to prevent or treat bradycardia or heart block may be included.

- 20. Is receiving a medication known to prolong the QT interval.
- 21. Has a history of clinically significant hypokalemia or hypomagnesemia that cannot be adequately controlled by supplementation.

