### 11.6.6 12-Lead Electrocardiograms

Triplicate 12-lead ECGs will be obtained after the patient has been resting for at least 5 minutes. For clinically significant ECG findings, a follow-up ECG should be performed within 24 hours and again 7 days later to ensure that the abnormality is not worsening. Follow-up 12-lead ECGs may be performed locally and sent to the Investigator for assessment; the Investigator will submit all ECGs done locally to the central ECG vendor.

A core ECG laboratory will manage all ECG monitoring activities. All ECG results along with the investigator's interpretation, including the average of triplicate measurements at each timepoint, will be presented in data listings.

QT values will be presented with the implementation of corrections (i.e., Fridericia's) as defined in International Council for Harmonisation (ICH) Guidelines E14 by the following categories:

Absolute QT interval corrected for heart rate based on Fridericia's formula (QTcF) interval prolongation:

- QTcF interval <450 ms
- QTcF interval 450-480 ms
- QTcF interval 480-500 ms
- QTcF interval >500 ms

Change from baseline in QTcF interval:

- QTcF interval increases from baseline 30-60 ms
- QTcF interval increases from baseline >60 ms

In addition, potential QT prolongations will be categorized as:

- PR interval >300 msec
- QRS duration >140 msec
- PR interval increase from baseline >50%
- QRS duration increase from baseline >40%

- HR increase >65% from baseline
- HR decrease >40% from baseline

The actual values and change from baseline values at each time point will be summarized for the safety populations. The overall interpretation will also be summarized by timepoint as well as the worst post-baseline.

The average of the triplicates at each timepoint will be used in the summaries as defined in [Section 9.2](#).

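### The PR >300 msec action trigger and SAP category ignore Baseline, so a device-protected patient admitted with PR already above 300 msec meets both with no change

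*Protocol*

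**What the plan says.** **Entry.** Exclusion 16 (protocol synopsis and 4.1.2) rules out, among other Screening ECG findings, first "degree AVB (PR interval >220 msec), QRS >120 msec, heart rate (HR) <50 beats per minute (bpm". Its Note makes an exception for first-degree AV block with PR of 220 msec or more: patients "who are treated prophylactically with an allowable implanted device are not excluded from the study". The Note to Exclusion 19 indicates what an allowable device is: "Patients with implanted univentricular pacemakers that are used prophylactically to prevent or treat bradycardia or heart block may be included". Neither Note gives an upper PR limit.

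**Action during the study.** Section 6.3.4.2 asks for Medical Monitor consultation on "PR interval >300 msec, QRS duration >140 msec, or any increase from baseline in PR or QRS greater than 50% or 40%, respectively", and for a repeat ECG. It continues: "If the event persists or worsens, study drug may be interrupted for 2 to 3 days". Dosing may resume if the finding has improved. If it persists or worsens after the interruption, the Investigator and Medical Monitor decide on permanent discontinuation. Section 4.4.1 likewise leaves ECG findings other than QT prolongation to Investigator discretion.

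**The same pathway in the synopsis.** Under Safety Assessments, interruption is mandatory if the finding persists or worsens on repeat. After the interruption: "If the abnormality has resolved (i.e., return to baseline values), study drug dosing may resume at the same dose". If the condition persists or worsens, permanent discontinuation is mandatory.

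**Analysis.** SAP 11.6.6 has a category "PR interval >300 msec" with no condition on the Baseline value. A PR increase of more than 50% from baseline is a separate category.

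**The concern.** Section 6.3.4 says that ECGs after entry are meant to detect changes in cardiovascular parameters. An absolute cut-off does that only if nobody can enter above it. For patients without a device, the 220 msec entry limit ensures this at Screening. For device patients, nothing does.

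Two things follow for a patient who enters above 300 msec. First, a value that the protocol accepted at enrolment starts an ECG action pathway, and the synopsis version of that pathway can end in permanent discontinuation. Second, the patient is counted in the PR category after Baseline, on placebo or active drug, although nothing has changed. Conduction disease is the cardiac concern that protocol section 1.2 stresses in this population, and the arms are small enough for one such count to alter the picture.

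**Working it through.** There is no plan figure to reproduce; the check is to apply the written rules to unchanged values.

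**Inputs.** Trigger: PR >300 msec, or a rise from baseline of more than 50% (6.3.4.2 and synopsis). Device exception: PR of 220 msec or more, no ceiling (4.1.2). Size: about 30 patients randomized 1:1:1 (3.1.1), so 30/3 = 10 per arm and 20 on active drug.

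**Step 1: which unchanged entry values trigger?** The absolute limb is met when entry PR exceeds 300. The relative limb is met only above 1.5 × entry PR.

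| Entry PR, unchanged (msec) | PR >300 met? | Rise needed to reach 300 | PR at +50% (msec) |
|---|---|---|---|
| 220 | No | 300/220 − 1 = 36.4% | 330 |
| 280 | No | 300/280 − 1 = 7.1% | 420 |
| 300 | No | 0% | 450 |
| 310 | Yes | already above | 465 |
| 330 | Yes | already above | 495 |

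Only entry values above 300 msec trigger with no change.

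**Step 2: follow an unchanged 310 msec through each pathway.**

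| Step | Synopsis | Section 6.3.4.2 |
|---|---|---|
| 310 on a scheduled ECG | Consult, repeat ECG | Consult, repeat ECG |
| Still 310 on repeat | Interruption mandatory | Interruption optional |
| Still 310 after interruption | At baseline, so resolved: may resume. Still above 300, so persists: permanent discontinuation | Not improved, so persists: Investigator and Medical Monitor decide |

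The synopsis gives two outcomes for one value. The documents also differ on whether interruption and discontinuation are mandatory, and on whether resumption needs a return to baseline or an improvement.

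**Step 3: effect on the SAP count.** One such patient adds 1/10 = 10 percentage points to an arm's PR >300 msec rate, or 1/20 = 5 points to pooled active. The chance that a single such patient is on active drug is 20/30 = 66.7%. If treatment continues, the value recurs at each of the five scheduled post-baseline double-blind ECG sets: Visit 3 (2) + Visit 4 (1) + Visit 5 (2) = 5.

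**Step 4: the number of such patients.** The documents do not give it. I assume 0 to 2 of 30. With all of them in one arm, the contribution to that arm is 0 to 20 percentage points.

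**Step 5: was the trigger revisited?** The Amendment 4 summary lists the device exception under Exclusion 16 and, for 6.3.4.2, only ECG timing around PK draws. Nothing listed shows the PR trigger being reconsidered for the newly admitted patients. Because that summary omits synopsis changes, this is suggestive only.

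**The case against.** The best reply is that the protocol body already copes. In 6.3.4.2 the trigger leads to a consultation and a repeat ECG. Sections 4.4.1 and 6.3.4.2, and 4.4.2 for the OLE, leave stopping to judgment, and a known, unchanged value is what judgment can handle. This stands for the body text: a reader might infer that the trigger is a drug-stopping rule throughout, and it is not. It does not remove the synopsis, which is written as mandatory.

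It can also be said that the synopsis defines resolved as a return to baseline values, so an unchanged value counts as resolved. That is a fair reading. Even so, mandatory interruption has already occurred, and the trigger is met again at the next ECG.

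On the SAP side, the increase of more than 50% is a separate category, actual values and changes from baseline are summarized, all ECGs are listed, and there is a placebo arm and no formal safety testing. A reader could therefore find the case. The PR >300 msec count itself still mixes pre-existing with new findings.

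Finally, the Investigator may exclude a patient as unsuitable (Exclusion 31), and Baseline ECGs are reviewed for exclusionary findings (6.3.4). Neither sets a PR ceiling, though both make such a patient less likely.

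**Conclusion.** The point holds narrowly. A device-protected patient with entry PR above 300 msec meets the action trigger and the SAP category with no change, and the synopsis gives that patient no single answer. Each such patient is worth about 10 percentage points of one arm's PR count, assuming 10 per arm. Whether any exists is unknown, so this is an inexpensive improvement rather than a threat to the trial's conclusions.

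Four stronger readings are not supported:
- **Any entry PR of 220 msec or more triggers.** Unchanged values of 220 to 300 msec do not.
- **The same gap affects QRS >140 msec.** QRS above 120 msec at Screening is excluded, and the device exception covers only first-degree AV block.
- **Stopping one such patient loses a tenth of the arm's primary-endpoint data.** The estimand follows a treatment policy strategy (protocol 9.1.1), the Early Termination visit repeats the Visit 5 efficacy assessments (7.2.5), and SAP 11.4.2.1.1 assigns termination data collected after Week 7 to Week 11. Loss is possible after a very early stop, but it is not shown.
- **The SAP attributes the count to study drug.** It tabulates the category and makes no causal claim.

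**What to change.** **SAP 11.6.6.** Count PR >300 msec as a post-baseline outlier only when the Baseline mean of the ECG replicates did not already exceed 300 msec. List patients who exceeded it at Baseline separately, by arm, with every post-baseline PR and its change from baseline. The listing is needed because, for example, a patient rising from 310 msec to any value up to 465 msec (310 × 1.5) would otherwise fall in neither PR category. An unchanged entry value above 300 msec would then add 0 instead of 1 to the count.

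**Protocol.** Reconcile the Exclusion 16 Note, the synopsis ECG pathway, 4.4.1 and 6.3.4.2 on two matters: whether interruption and discontinuation are mandatory or discretionary, and how resolved (a return to baseline values), improved and persists apply to a value unchanged from entry. The threshold and the clinical rule are for the sponsor to set.

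**Cost.** One SAP condition on data already collected, one extra listing, a possibly lower raw PR count that should be footnoted, and a short protocol clarification.
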